### **Analytic and Design Considerations**

1) Latinos in the Houston Metropolitan area are heterogeneous with respect to country of origin (or national identity). We recognize the challenge of developing an intervention that adequately accounts for differences associated with this heterogeneity. We considered focusing on one or two groups e.g., Mexicans & Mexican Americans. However, we selected to focus on various national origins in order to take advantage of the unique opportunity for developing an intervention with the greatest potential for generalizability to Latinos of all origins. Houston is an ideal geographic locale for conducting this research since Latino subgroups are well represented in the population. In one of our previous studies (*Project Impact 1*), Latinos across national origin groups were found to be similar on key demographic and smoking related variables including. Also, investigators have previously identified values and characteristics that are shared among Latino sub-groups in the U.S., providing a rationale for developing an intervention relevant to multiple Latino subgroups.

- 2) Despite our randomized design, it is possible that baseline participant characteristics that are potential confounders may be unevenly distributed. This potential problem will be closely monitored and adjustments to the statistical analysis plan will be made if necessary.
- 3) Our primary research question compares the three treatment groups (CTSC, CTSC+AE, & HE) on the mean percentage of days of NRT adherence during the 12 weeks of treatment. In our preliminary study of Latino smokers (*Project Impact 1*) we found that on average participants were adherent on 46.7% (SD=36) of days during the 12 weeks of NRT treatment. Based on this finding, we estimate that our control condition (HE) will show a similar rate of NRT adherence (adherent on 56% of treatment days). We are guided primarily by our expectations that clinically significant improvements in outcomes will be achieved with >75% adherence and we base our estimate of the NRT adherence rate for our CTSC+AE condition on two studies reporting NRT adherence rates for interventions that sought to increase adherence but did not exclusively target adherence. The adherence rates of the experimental condition in these studies ranged from 88-93%. The current study is not only designed to test the feasibility of CTSC and CTSC+AE (Aim 1), but to evaluate the CTSC+AE intervention compared to HE and CTSC groups. It is not expected to be a definitive efficacy trial and the proposed sample will yield power to detect only large effects. Due to the limited scope of this development project, this study will not be powered for formal hypothesis testing of group differences. Nevertheless, the proposed study will conduct analyses investigating distributional assumptions and co-variation among examined predictors which will inform the design of a future efficacy trial that will be fully powered.
- 4) Other smoked non-tobacco substances can potentially interfere with our carbon monoxide testing. To address this concern, prior to all CO testing, participants will be asked whether they have smoked non-tobacco substances in the last two days. If so, the participant will be asked to provide an additional CO sample after 2 days of non-tobacco substance abstinence.
- 5) The two treatment interventions are not completely time-matched and participants in the CTSC+AE condition will receive a slightly greater dosage of the behavioral intervention than CTSC and HE. Therefore, dosage effects may confound our results. In designing our study, we considered this limitation. However, we made a decision to prioritize a design where the control condition (HE) reflects a minimum standard of care for individuals undergoing NRT treatment so that we can assess the real-world clinical implications of our intervention.
- 6) Missing Data: An intent-to-treat analysis will be utilized to account for missing data. We will assume non-adherence and/or smoking relapse on days for which we do not have data. Exhaustive efforts will be made to schedule visits so as to minimize such instances.

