## 4.0 Patient Eligibility

**Participants & Recruitment:** A total of 36 participants will be enrolled, 12 in each condition. We will recruit participants by posting flyers at locations in the greater Houston area that are known to be frequented by our target Latino population (ex: community centers, Hispanic food markets and grocery stores, salons, bus stations, clinics serving mainly Hispanics). We will also post ads in free Houston area Spanish language print newspapers (ex: La Subasta, Buena Suerte) as well as use radio ads heard throughout the greater Houston area. All ads and flyers will use the IRB approved advertisements. (See Appendix R).

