*Bicultural Involvement Scale (BIS)* (Appendix K) is a 24-item self-report measure used to assess cultural orientation. The measure generates scores for individuals' independent association with each of the two cultures, their degree of biculturalism, and a rating of their total cultural involvement. Originally developed for use with Hispanic and American individuals, the measure has also been modified for use with individuals from other cultures, including Asia and Australia. Adapted from the acculturation scale, the bicultural involvement questionnaire was developed by José Szapocznik, William M. Kurtines, and Tatjana Fernandez in 1980 as a multidimensional tool for measuring cultural orientation. Unlike the majority of acculturation measures that preceded it, the BIQ does not assume that involvement in one culture necessitates exclusion of association with another.

*Smoking Status* will be assessed at each study visit. Self-reported abstinence will be verified using expired carbon monoxide testing using a Bedfont Micro+ Smokerlyzer® at the 2 and 6-week sessions and 3 and 6-month follow-up assessments.

**Randomization:** After the Baseline Visit, participants will be randomly assigned to CTSC, HE, or CTSC+AE using a standard urn randomization technique (1:1:1) stratified by gender.

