## 11.0 Statistical Considerations

**Proposed Analyses:** In this pilot study, we will summarize descriptive statistics to characterize our study sample and describe between group differences. Descriptive statistics will be tabulated for all study variables which includes demographics, measures of intervention acceptability, feasibility, fidelity, and smoking history, nicotine dependence, and other variables.

We also plan to conduct basic effect size estimates to derive preliminary findings based on pre/post design. With such a small sample size, we will focus on the substantive magnitude of observed between group differences. We will, however report Fischer's exact p-values and the nonparametric Kruskal-Wallis test for equality of rank-ordered population distributions when comparing treatment groups on categorical and continuous outcomes, respectively. Graphical methods will also be used to explore and describe the association between adherence to treatment and smoking in each of the intervention groups.

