**Aim 1:** Evaluate the feasibility, fidelity, and acceptability of the CTSC and CTSC+AE in Latino smokers. Our evaluation of these domains will seek to identify elements of the intervention that are successful or in need of improvement for a planned larger trial. To evaluate these domains we will assess: 1) Recruitment and retention of participants 2) Intervention adherence 3) Program satisfaction 4) The extent to which the intervention was delivered as planned (derived from the Fidelity Checklist [Appendix Z], described in the measures section).

**Aim 2:** To evaluate the preliminary efficacy of the CTSC and CTSC + AE, as compared to HE, on increasing biochemically verified 7-day point prevalence smoking abstinence smoking abstinence rates at 3 and 6 month follow-up in Latino smokers. We hypothesize that participants in the CTSC + AE group will demonstrate significantly greater rates of biochemically verified 7-day smoking point prevalence abstinence at 3 and 6-month follow-up

**Aim 3:** To evaluate the efficacy of the CTSC+AE condition, as compared to the HE and CTSC groups, on increasing adherence to nicotine patch treatment (NRT adherence is defined as the proportion of days of NRT use over the number of patches made available).

**Aim 4 (Exploratory):** To examine potential mediators and moderators of the relationship between our primary outcomes (Aims 1-3) and our treatment groups. For this exploratory aim we will examine several variables that may influence treatment outcomes including gender, age, alcohol use, health related fatalism, sense of control and acculturation.

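### The rule for covariate adjustment is open-ended and not shielded from outcome data, and the planned treatment comparisons leave out the gender strata used in randomisation

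*Combined protocol and SAP*

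**What the plan says.** Allocation (section 5.0, Randomization) is made "using a standard urn randomization technique (1:1:1) stratified by gender". On size, section 4.0 states: "A total of 36 participants will be enrolled, 12 in each condition".

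The between-group analysis in section 11.0 is mainly descriptive: "With such a small sample size, we will focus on the substantive magnitude of observed between group differences". It then adds: "We will, however report Fischer's exact p-values and the nonparametric Kruskal-Wallis test". Neither test is described as stratified or adjusted.

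Item 2 of the Analytic and Design Considerations accepts that "it is possible that baseline participant characteristics that are potential confounders may be unevenly distributed", and continues: "This potential problem will be closely monitored and adjustments to the statistical analysis plan will be made if necessary". That is the whole rule.

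Gender returns only under exploratory Aim 4, in a list of candidate mediators and moderators "including gender, age, alcohol use, health related fatalism, sense of control and acculturation". These are examined by descriptive, chi-square and correlational methods, not within the treatment comparison.

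Two statements in section 12.0 bear on timing. Under Data Quality and Integrity, preliminary analyses start soon after data collection begins. Under Data Safety and Monitoring by Study Personnel, data are entered into REDCap only once all have been collected.

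**The concern.** A rule that reopens the analysis plan when the arms look different leaves three things undecided: what counts as different, which variables may enter, and what model replaces the planned tests. The last is not a detail. Fisher's exact and Kruskal-Wallis take no covariates, so any adjustment means moving to a method that the plan never describes.

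If that move is made after outcomes have been seen by arm, there are several possible answers and room to prefer the most favourable. Section 12.0 does not rule this out. What is exposed is the size of the between-arm differences, which the plan makes its focus and wants to carry into a larger trial, and the p-values reported beside them.

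The gender strata are a smaller, separate matter. Leaving a stratification factor out of the analysis generally costs precision rather than validity, but it is the one covariate that could have been fixed in advance without debate.

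**Working it through.** The plan gives no figure for imbalance or adjustment, so there is nothing of its own to reproduce. The detectable difference in section 11.0 plays no part here.

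**Inputs from the documents.** Three arms of 12 (section 4.0); two-sided alpha 0.05 (section 11.0); six Aim 4 variables, or five without gender, used here as stand-ins for the adjustment covariates. The missing-data rule (item 6) counts missing days as non-adherence or smoking, so all 36 stay in the analysis.

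**Assumptions not in the documents.** Normal covariates, independent or correlated 0.3 with each other; an imbalance trigger of 0.5 SD; covariate–outcome correlations of 0.25–0.35; no missing baseline data; a three-group F-test standing in for the planned tests.

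**1. Chance of imbalance.** The SD of a standardised difference between two arms is √(2/12) = 0.41. By simulation, one given covariate differs by more than 0.5 SD between some pair of arms in 46.3% of trials. For several independent covariates:

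- five: 1 − (1 − 0.463)^5 = 95.5% (simulated 95.1%; 93.3% if correlated 0.3)
- six: 1 − (1 − 0.463)^6 = 97.6% (simulated 97.4%; 96.5% if correlated 0.3)

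A stricter trigger changes the picture:

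- a difference above 0.8 SD on at least one of five: 52–56%
- a baseline test with p < 0.05 on any of five or six: 1 − 0.95^5 = 22.6% and 1 − 0.95^6 = 26.5% if independent (simulated 21–27% overall)

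**2. Type I error by adjustment rule.** Simulation with six independent covariates, each correlated 0.25–0.35 with the outcome, and no treatment effect:

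| Rule | Type I error at nominal 5% |
|---|---|
| Unadjusted | about 5% |
| Two covariates fixed in advance | about 5% |
| Adjust for every covariate differing by more than 0.5 SD, without regard to outcome | about 1–4% |
| Smallest p among the unadjusted model and models adjusting for imbalanced covariates | about 9–10% |

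If the analyst may also choose covariates that are not imbalanced, the last row becomes 10–14% (coefficients 0.15 and 0.3).

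**3. What a fixed covariate buys.** With 36 participants, three arms and one covariate correlated r with the outcome, the standard error is multiplied by about √[(1 − r²)(1 + 1/(36 − 3 − 2))] = √[(1 − r²) × 1.032]:

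- r = 0.5: √(0.75 × 1.032) = 0.880, a 12% reduction
- r = 0.3: √(0.91 × 1.032) = 0.969, a 3% reduction
- r = 0: √1.032 = 1.016, a loss of about 1.5%

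Simulation of the same setting agrees (12.1%, 3.2% and −1.6%). The main gain is a settled analysis; precision is secondary.

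**The case against.** The plan's wording is conditional: imbalance is called possible, and changes follow only if needed. The trigger is baseline imbalance, not outcome, and acting on baseline alone does not inflate type I error; in the simulation it made the test conservative. The 0.5 SD threshold and the covariate list are not in the documents, and gender, one of the six Aim 4 variables, is protected by the stratified urn. The study is a pilot that disclaims formal testing, so type I error is a weak yardstick.

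Most of this stands, and it rules out four stronger readings that a reader might infer:

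- *The final model will be chosen from the data.* The text permits this but does not commit to it.
- *Imbalance is nearly certain.* That holds for a 0.5 SD trigger over five or six covariates, not for one given covariate or a significance-test trigger.
- *The rule itself inflates type I error.* Inflation needs selection with outcomes visible.
- *An unmasked team will make the decision.* The documents do not say who decides or what they will know.

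The pilot argument does not dispose of the point. Section 11.0 still reports p-values, states a detectable difference at a two-tailed 0.05 level, hypothesises significantly greater abstinence with CTSC+AE, and calls the adherence comparison the primary research question. Effect estimates are open to selective adjustment whether or not a p-value is read.

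**Conclusion.** The point holds in limited form. The adjustment rule has no covariate list, threshold, model or decision point. The two statements in section 12.0 do not agree on whether outcomes could be seen before it is applied. The treatment comparisons do not use the gender strata.

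An occasion to invoke the rule will be common under a loose definition of imbalance (93–97%) and uncommon under a strict one (21–27%). The harm depends on how it is used: about 9–10% type I error if the best result is picked with outcomes visible, about 1–4% if applied mechanically, and 5% with a fixed set. These figures rest on the assumptions listed with the calculation. Either use of the open rule departs from the nominal level; fixing the covariates does not. This should be corrected, but it does not invalidate the trial.

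**What to change.** Replace the adjustment sentence in item 2, before any outcome is seen by arm, with:

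> Between-arm differences in NRT adherence will be estimated with a linear model adjusting for gender (stratification factor) and baseline FTND, whatever the observed imbalance, with a gender-stratified rank test for the p-value. Abstinence will be compared with an exact test stratified by gender. The unadjusted Kruskal-Wallis and Fisher's exact results will be shown alongside. Any other covariate adjustment will be labelled a sensitivity analysis.

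Also reconcile the two statements in section 12.0: say when data are entered, and whether the preliminary analyses show outcomes by arm.

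FTND is proposed because it is already measured at the baseline visit. The documents give no evidence that it predicts patch adherence, and it is not on the Aim 4 list; another baseline measure would serve equally well if named now.

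**Cost.** No new visit or measure. It uses one or two degrees of freedom and takes slightly more analysis work, because methods that can adjust or stratify must be added to the planned tests. The standard error falls by about 3% at r = 0.3 and 12% at r = 0.5, and rises by about 1.5% if FTND is unrelated to the outcome.

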## 12.0 Data and Protocol Management

### Data Safety and Monitoring by Study Personnel

We have developed a data and safety monitoring plan for this project that is commensurate with the risks posed by the project. Data and safety monitoring for this project will consist of ongoing monitoring by the PI and research personnel. The plan includes procedures for:

1. Monitoring the progress of the trial and safety of the participants
2. Assuring compliance with the requirements for reporting of adverse events (AEs)
3. Assuring that any action resulting in a temporary or permanent suspension of a study is reported to the NIH official who is responsible for the grant
4. Ensuring data accuracy and protocol compliance.

The procedures for monitoring progress, safety, reporting of AEs, and assuring that actions resulting in suspension of the study are reported to the NIH are described in the sections below under *IRB Monitoring* and the *Guidelines for Filing Reports of Adverse Experiences at MDACC*. Plans and procedures for ensuring data quality and integrity are described in the final section entitled *Data Quality and Integrity*.

Study data will be collected using traditional hardcopy pen and paper. Once all data has been collected, it will be entered into REDCap (Research Electronic Data Capture). REDCap ([www.project-redcap.org](http://www.project-redcap.org)) is a secure, web-based application with controlled access designed to support data capture for research studies, providing: 1) an intuitive interface for validated data entry; 2) audit trails for tracking data manipulation and export procedures; 3) automated export procedures for seamless downloads to common statistical packages; and 4) procedures for importing data from external sources. REDCap (<https://redcap.mdanderson.org>) is hosted on a secure server by MD Anderson Cancer Center's Department of Research Information Systems & Technology Services.

REDCap has undergone a Governance Risk & Compliance Assessment (05/14/14) by MD Anderson's Information Security Office and found to be compliant with HIPAA, Texas Administrative Codes 202-203, University of Texas Policy 165, federal regulations outlined in 21CFR Part 11, and UTMDACC Institutional Policy #ADM0335. Those having access to the data file include the study PI and research team personnel. Users are authenticated against MDACC's Active Directory system. External collaborators are given access to projects once approved by the project sponsor. The application is accessed through Secure Socket Layer (SSL). All protected health information (PHI) will be removed from the data when it is exported from REDCap for analysis. All dates for a given participant will be shifted by a randomly generated number between 0 and 364, thus preserving the distance between dates. Dates for

each participant will be shifted by a different randomly generated number. Following publication study data will be archived in REDCap.

**Human Subjects Involvement and Characteristics** Participants will be 36 Latino smokers at least 18 years of age that are interested and motivated to quit smoking. The following inclusion criteria will be used: 1) Adults at least 18 years of age; 2) Current smoker (>5 cigarettes per day for the past 3 months) 3) Able to speak and read English or Spanish 4) Agree to participate in the study and be available for 6 weeks of treatment and 6 months of follow-up 5) Willing to set a quit date within 2 weeks of enrollment date 6) Identify as being of Latino heritage, ethnicity, or ancestry. Exclusion Criteria includes: 1) Individuals suffering from any unstable medical condition precluding the use of NRT 2) Currently using smokeless tobacco, electronic nicotine delivery systems (ENDS), nicotine replacement therapy, or other smoking cessation treatment 3) Pregnant or nursing 4) Suffering from a severe psychiatric disorder (assessed using self-reporting history of psychiatric diagnosis during the phone screening) that would interfere with participation 5) Diagnosis of substance dependence other than nicotine, screened using the Diagnostic and Statistical Manual of Mental Disorders, Fourth Edition (DSM IV TR) criteria 6) Individuals that do not have access to a working telephone.

**Sources of Materials** Data will be obtained through self-report questionnaires, interview questionnaires, and intervention session audio recordings. In addition, participants will be administered a test of expired air carbon monoxide level by a trained research assistant.

**Adverse Events** Given the non-invasive, minimal risk nature of the proposed research, we anticipate that the types of adverse experiences that may occur, if any, will focus on concerns about the discomfort of nicotine withdrawal or possible distress associated with sensitive issues arising during data collection. The study includes procedures to minimize these risks.

**Adverse Experiences Associated with Nicotine Abstinence/Withdrawal:** Participants may experience nicotine abstinence/withdrawal effects. These effects may include irritability, difficulty concentrating, insomnia, anxiety, dysphoria, and increased hunger. None of these effects result in serious adverse health consequences.

**Adverse Experiences Associated with Self-Report:** This study will also involve the use of questionnaires and interviews that could reveal sensitive information (e.g., assessment of mood disturbance). The instruments are

not used to communicate psychiatric diagnosis to the participant and procedures are in place to protect participant confidentiality. However, if a mood disorder is suspected, the participant may be contacted. Possible outcomes of this contact could include referral to the participant's primary care physician and/or other physician, and/or other mental health providers.

***Adverse Experiences Associated with Nicotine***

***Replacement Therapy (NRT) Patch*** The nicotine patch may cause nausea and/or headache. Participants may feel dizzy and/or light-headed, may be moody and/or have trouble sleeping. Participants may also have an allergic reaction to the patch that results in red, itchy, and/or sore skin around the patch.

***Adverse Experiences Requiring Immediate Reporting***

Two types of Adverse Experiences require prompt reporting to the Institutional Review Board (IRB) and the study sponsor: Serious Adverse Experiences and Unexpected Adverse Experiences. For serious or unexpected AEs, a written report is submitted to the Office of Protocol Research (OPR) within 10 working days of the adverse experience. Unexpected fatal or life-threatening experiences are telephoned immediately to the OPR and the OPR will notify the appropriate sponsors within 3 days. For AEs that are not serious or not unexpected, written reports are submitted to OPR every month.

***Serious Adverse Experiences*** For the majority of trials performed at MDACC, a serious adverse experience is a clinical event occurring subsequent to the administration of an agent or intervention which can be characterized as fatal, life-threatening, permanently disabling, requiring hospitalization, or an overdose.

***Unexpected Adverse Experience*** An unexpected adverse experience is a clinical event that is not identified in nature, severity, or frequency in the investigator's brochure, protocol, or other pertinent supporting literature. At times, the occurrence of an unexpected adverse experience might not be suspected until more than one event has occurred. Once the clinical event has been identified, all cases should be reported.

***Informed Consent*** Those who agree to participate will

give informed consent. A written consent form will be presented and read to the potential participant, and an opportunity will be provided to review the form and to have any questions answered before the form is signed and filed. Consent forms contain a description of all procedures involved in the study, the risks and benefits associated with the research, the rights of the participant (e.g. right to withdraw) and the potential limits of confidentiality (e.g. assessed suicidal or homicidal risk). We have included additional safeguards for consenting non-English speaking participants in the protocol, due to the expected number of Spanish monolingual speakers. These include having the RA complete the training course for consenting non-English speaking subjects and have access to the course in the future if needed as a refresher. The PI will also meet with the RA once a month to discuss any concerns associated with the informed consent process. The RA will also alert the PI or research coordinator immediately if any questions or problems arise relating to the informed consent of participants. Additionally, the PI or his designee will observe 1 informed consent conducted by the RA per month.

**Data Quality and Integrity** Due to the ongoing monitoring of the project, study investigators and staff will maintain quality assurance procedures for all data. Several procedures will be used to maintain the integrity of the data. All databases will be stored in a centralized location on one of the departmental servers, which is backed up daily, with access limited to specific users at the discretion of the PI. Hard copy data sources will be stored under lock and key in the Department of Health Disparities Research. Electronic data will be maintained by numerically coding of all data and by password-protecting computer files. Data will be stored on a secure server with a firewall to protect the data and to prevent unauthorized access. Databases on the server will be password protected and will be accessed only by research staff members who have met the MDACC IRB's requirement for training in Human Subjects Protections. Data transmissions to and from the data server will be encrypted. All participants will be assigned a unique identification code that will be stored separately from identifying information. Audio recordings of visits will be collected using a digital recording device (DRD). Once an interview session is completed a research assistant under the supervision of [name]

will immediately upload the audio recording to a secure departmental server. The DRD that was used for the interview will then be erased of the recording. Audio recordings on the secure server will be password protected and maintained and monitored on the secure server. Participants will be given full access to their data, if formally requested, after the completion of the study. Privacy safeguards will include appropriate password protection and physical security for all computer systems. Additional quality assurance procedures will include a data collection protocol as well as regularly scheduled meetings among the investigators and project staff to review problems and solutions, and discuss concerns. Data entry systems will specifically provide field checks, range checks for continuous variables, and valid value checks for categorical variables; checks for legitimate dates and times and logical consistency. Preliminary analyses will be initiated shortly after data collection begins to allow monitoring. All research staff involved in the study will be carefully supervised by [name], and frequent team meetings will be held to assure that proper protocol is being followed.

